### 3. OBJECTIVES AND ENDPOINTS

**Table 4** presents the objectives and endpoints.

**Table 4: Objectives and Endpoints**

Objectives	Endpoints
Primary	
To establish the efficacy of ruxolitinib 1.5% cream BID in participants with HS.	Change from baseline in AN count at Week 16.
Secondary	
To further evaluate the treatment effect of ruxolitinib 1.5% cream BID in participants with HS.	

Proportion of participants achieving AN50, AN75, AN90, and AN100 (at least 50%, 75%, 90%, and 100% reduction respectively in AN count relative to baseline) at Week 16.

Change from baseline in the Skin Pain NRS score at Week 16.

Change from baseline in the Itch NRS score at Week 16.

Proportion of participants who achieve HiSCR at Week 16. Note: HiSCR is defined as at least 50% reduction in AN count with no increase in either abscess or draining fistula counts, relative to baseline.

Change from baseline in the International Hidradenitis Suppurativa Severity Score System (IHS4) score at Week 16. Note: IHS4 score is calculated by the number of inflammatory nodules (multiplied by 1) plus the number of abscesses (multiplied by 2) plus the number of draining tunnels (multiplied by 4).

To evaluate the safety and tolerability of ruxolitinib 1.5% cream BID in participants with HS.	The type, frequency, and severity of AEs, and changes in vital signs and hematology and serum chemistry parameters.

**Table 4: Objectives and Endpoints (Continued)**

## 4. STUDY DESIGN

### 4.1. Overall Design

This is a Phase 2, randomized, DBVC study in participants  $\geq 18$  years of age with confirmed diagnosis of HS. The study will consist of a 16- week DBVC period followed by a 16-week OLE period.

Participants will be screened for up to 28 days prior to the first application of ruxolitinib 1.5% cream or vehicle cream. Key entry criteria for participants are diagnosis of HS (Hurley Stage I or II) for at least 3 months before screening visit and a **total AN count of 3 to  $\leq 10$  with no draining tunnels** at screening and baseline. The AN count of 3 may affect at least 1 distinct anatomical area; however, an AN count of  $> 3$  to  $\leq 10$  must be affecting at least 2 distinct anatomical areas.

Approximately 60 eligible participants  $\geq 18$  of age will be randomized 1:1 to either ruxolitinib 1.5% cream or vehicle cream (see [Figure 1](#)). Participants will be stratified by baseline AN count ( $\geq 3$  to 4 or  $\geq 5$  to 10). Participants will apply either ruxolitinib 1.5% cream or vehicle cream (both BID) through Week 16 to the all affected areas identified at baseline.

At Week 16, participants who meet the criteria (compliant with the Protocol and without safety concerns) will enter the 16-week OLE period. Participants randomized to vehicle BID in the DBVC period will be crossed over to ruxolitinib 1.5% cream BID and participants randomized to ruxolitinib 1.5% cream BID at baseline will remain on ruxolitinib 1.5% cream BID through Week 32 in an open-label fashion. At Week 16, the HS treatment area will be evaluated by the investigator to assess the disease and confirm whether treatment continuation is required (AN count  $\geq 1$  and/or Skin Pain NRS  $\geq 1$ ) during the OLE period or can otherwise (re)enter an observation/no treatment cycle (AN count = 0 and Skin Pain NRS = 0). During the OLE, participants will only treat symptomatic lesions (eg, presence of AN lesion(s) and/or pain) including new lesions not exceeding 20% BSA. Treatment assignment during the DBVC period will remain blinded to investigators and participants until after all participants have completed the study or discontinued and completed the safety follow-up period.

During the DBVC and OLE periods, participants who require and are treated with lesional rescue interventions (eg, incision and drainage or intralesional corticosteroid injection), are considered nonresponsive to therapy, and will be discontinued from the study.

[Figure 1](#) presents the study design schema, and [Table 3](#) presents the SoA. Adherence to the study design requirements, including those specified in the SoA, is essential and required for study conduct.

The COVID-19 global pandemic may present challenges to the normal conduct of this study (including AE and laboratory assessments), requiring the implementation of potential mitigation strategies described in [Appendix B](#).

## **4.2. Overall Study Duration**

The study begins when the first participant signs the study ICF. It is estimated that an individual will participate for approximately 40 weeks, including up to 28 days for screening, 16 weeks for treatment during the DBVC period, 16 weeks for treatment during the OLE period, and up to 30 days for follow-up after the last application of study treatment.

The end of the study is defined as the date of the last visit of the last participant in the study. A participant is considered to have completed the study if they have completed all study visits, including the safety follow-up visit

## **4.3. Study Termination**

The investigator retains the right to terminate study participation at any time, according to the terms specified in the study contract. The investigator is to notify the IRB/IEC of the study's completion or early termination in writing, send a copy of the notification to the sponsor or sponsor's designee, and retain 1 copy for the site study regulatory file.

The sponsor may terminate the study electively if, for example, required by regulatory decision. If the study is terminated prematurely, the sponsor will notify the investigators, the IRBs and IECs, and the regulatory bodies of the decision and reason for termination of the study.

# **5. STUDY POPULATION**

Deviations from eligibility criteria are not allowed because they can potentially jeopardize the scientific integrity of the study, regulatory acceptability, and/or participant safety. Therefore, adherence to the criteria as specified in this Protocol is essential. Prospective approval of Protocol deviations to recruitment and enrollment criteria, also known as Protocol waivers or exemptions, are not permitted.

## **5.1. Inclusion Criteria**

Participants are eligible to be included in the study only if all of the following criteria apply:

1. Ability to comprehend and willingness to sign a written ICF for the study.
2. Male or female participants age 18 years or above.
3. Diagnosis of HS based on clinical history and physical examination for at least 3 months before screening visit.
4. Diagnosis of HS (Hurley I or II) with the following:
  - a. A total AN count of 3 to  $\leq$  10, with no draining tunnels at screening and baseline visits.  
AND
  - b. The AN count at the screening AND baseline visits:
    - AN of 3 should affect at least 1 distinct anatomical area
    - AN of  $> 3$  to  $\leq 10$  should affect at least 2 distinct anatomical areas

Note: Anatomical areas include but are not limited to left and right axilla; or left and right inguinocrural fold or inframammary areas.

5. Baseline Skin Pain or Itch NRS score  $\geq 1$ . Baseline Skin Pain or Itch NRS is defined as the 7-day average of Skin Pain or Itch NRS score before Day 1 (data from a minimum of 4 out of 7 days directly prior to Day 1 is needed).
6. Agreement to NOT use topical and systemic antibiotics for treatment of HS during the study.
7. Agreement to NOT use a diluted beach bath or topical antiseptic washes containing chlorhexidine gluconate or benzoyl peroxide on the areas affected by HS lesions during the study.
8. Willingness to avoid pregnancy or fathering children based on the criteria below.
  - a. Male participants with reproductive potential must agree to take appropriate precautions to avoid fathering children from screening through 90 days (a spermatogenesis cycle) after the last application of ruxolitinib cream and must refrain from donating sperm during this period. Permitted methods in preventing pregnancy (see [Appendix A](#)) should be communicated to the participants and their understanding confirmed.
  - b. Female participants who are WOCBP must have a negative serum pregnancy test at screening and before the first application on Day 1 and must agree to take appropriate precautions to avoid pregnancy from screening through 30 days (1 menstrual cycle) after the last application of study ruxolitinib cream and must refrain from donating oocytes during this period. Permitted methods in preventing pregnancy (see [Appendix A](#)) should be communicated to the participants and their understanding confirmed.
  - c. Female participants not considered to be of childbearing potential as defined in [Appendix A](#) are eligible.

## 5.2. Exclusion Criteria

Participants are excluded from the study if any of the following criteria apply:

1. Presence of draining tunnels at screening or at baseline visits.
2. Total HS BSA affected (excluding scalp) is  $> 20\%$ .
3. Participants with concurrent conditions and history of other diseases:
  - a. Active ongoing inflammatory diseases of the skin other than HS that might confound the evaluation of HS.
  - b. Any other concomitant skin disorder (eg, generalized erythroderma such as Netherton's syndrome), pigmentation, or extensive scarring that in the opinion of the investigator may interfere with the evaluation of HS AN or compromise participant safety.
  - c. Active tuberculosis; or current and/or history of latent tuberculosis unless adequately treated.
  - d. Immunocompromised (eg, lymphoma, acquired immunodeficiency syndrome, or Wiskott-Aldrich syndrome).
  - e. Chronic or acute infection requiring treatment with systemic antibiotics, antivirals, antiparasitics, antiprotozoals, or antifungals within 2 weeks before baseline.

- f. Active acute bacterial, fungal, or viral skin infection (eg, herpes simplex, herpes zoster, chicken pox, clinically infected AD, or impetigo) within 2 weeks before baseline.
    - g. Unstable asthma or COPD requiring systemic treatment (such as intravenous steroids) or hospital admission or emergency room treatment within 3 months from baseline; or stable asthma or COPD requiring more than 720 µg/day (2 puff BID of 180-ug dose) or fluticasone more than 440 µg/day (2 puffs BID of 110-ug dose) or other equivalent inhaled corticosteroids.
  4. Any serious illness or medical, physical, or psychiatric condition(s) that, in the investigator's opinion, would interfere with full participation in the study, including administration of study drug and attending required study visits; pose a significant risk to the participant; or interfere with interpretation of study data. For example:
    - a. Clinically significant or uncontrolled cardiovascular disease, including unstable angina, acute myocardial infarction, or stroke within 6 months from Day 1 of study drug application, New York Heart Association Class III or IV congestive heart failure, and arrhythmia requiring therapy or persistent uncontrolled hypertension (blood pressure > 150/90 mmHg) unless approved by medical monitor/sponsor.
    - b. Any malignancies or history of malignancies within 5 years before baseline with the exception of adequately treated or excised nonmetastatic basal cell or squamous cell cancer of the skin, or cervical carcinoma in situ.
    - c. History of severe anemia, severe thrombocytopenia, or severe neutropenia.
  5. Any of the following clinical laboratory test results at screening:
    - a. Cytopenias at screening, defined as follows:
      - Hemoglobin < 100 g/L (ie, 10 g/dL)
      - ANC < 1.5 × 10^9/L (ie, 1500/µL)
      - Platelet count < 1 × 10^11/L (ie, 100,000/µL)
    - b. Liver function tests:
      - AST or ALT ≥ 2.5 × ULN
      - Total bilirubin > 1.5 × ULN unless Gilbert's syndrome
    - c. Estimated GFR < 30 mL/min/1.73 m^2 (using the Chronic Kidney Disease Epidemiology Collaboration equation).
    - d. Positive serology test results at screening for HIV antibody.
    - e. History or current of acute or chronic active HBV or HCV infection. Participants who have recovered or have been successfully treated with no evidence of active HBV or HCV infection, and those who are immune due to hepatitis B vaccination can enroll. Participants who are positive for the hepatitis B surface antigen will be eligible if they are negative for HBV-DNA; participants who are positive for the anti-HCV antibody will be eligible if they are negative for HCV-RNA.
    - f. Any other clinically significant laboratory result that, in the opinion of the investigator, poses a significant risk to the participant.
  6. History of treatment failure (as assessed by the investigator through study participant interview) for HS or any other inflammatory condition with any systemic or topical JAK or TYK2 inhibitor (eg, abrocitinib, baricitinib, brepocitinib, deucravacitinib, filgotinib, lestaurtinib, pacritinib, ruxolitinib, tofacitinib, upadacitinib).

7. Use of any of the following treatments within the indicated washout period before the baseline visit:
  - a. 12 weeks or 5 half-lives (if known), whichever is longer, for systemic immunosuppressive or immunomodulating biologic drugs (eg, adalimumab, anakinra, bermekimab, bimekizumab, brodalumab, certolizumab, dupilumab, etanercept, golimumab, guselkumab, infliximab, iscalimab, ixekizumab, risankizumab, rituximab, secukinumab, vilobelimab, ustekinumab, etc).
  - b. 4 weeks for any topical or systemic JAK or TYK2 inhibitor (eg, abrocitinib, baricitinib, brepocitinib, deucravacitinib, filgotinib, lestaurtinib, pacritinib, ruxolitinib, tofacitinib, upadacitinib, etc).
  - c. 4 weeks – systemic corticosteroids or adrenocorticotropic hormone analogs, cyclosporin, methotrexate, azathioprine, or other systemic immunosuppressive or immunomodulating agents (eg, mycophenolate or tacrolimus).
  - d. 2 weeks or 5 half-lives, whichever is longer - strong systemic CYP3A4 inhibitors.
  - e. 2 weeks – systemic antibiotics and immunizations with live-attenuated vaccines, sedating antihistamines unless on a long-term stable regimen (nonsedating antihistamines are permitted).
- Note: Live-attenuated vaccines are prohibited during the DBVC period. COVID-19 vaccination is permitted.
- f. 2 weeks – topical therapy for HS (eg, topical antiseptics, topical antibiotics, topical corticosteroids, topical calcineurin inhibitors, other topicals).
- g. 2 weeks - any opioid treatment.
8. Current treatment or treatment within 30 days or 5 half-lives (whichever is longer) before the baseline visit with another investigational medication or current enrollment in another investigational drug Protocol.
9. Participant with known allergy or reaction to any of the components of the study cream.
10. History of alcoholism or drug addiction within 1 year before screening or current alcohol or drug use that, in the opinion of the investigator, will interfere with the participant's ability to comply with the administration schedule and study assessments.
11. Pregnant or lactating participants, or those considering pregnancy during the period of their study participation.
12. Participants with inadequate venous access in nonlesional areas or in lesional areas not treated by the study drug within the last 7 days.
13. Participants who are committed to a mental health institution by virtue of an order issued either by the judicial or the administrative authorities.
14. Participants who, in the opinion of the investigator, are unable or unlikely to comply with the administration schedule and study evaluations.
15. Employees of the sponsor or investigator or otherwise dependents of them.

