### **6.6.3. Prohibited Medications and Procedures**

No rescue therapy and/or procedural intervention is allowed for HS during the study. In addition, the following rescue therapies are not permitted during the study:

- Treatment known to affect the course of HS.
- Current opioid treatment.
- Topical or systemic antibiotics, topical or intralesional corticosteroids, topical calcineurin inhibitors, systemic corticosteroids, methotrexate, dapsone, metformin, tretinoids/retinoids, aldactone, cyclosporine A, azathioprine and biological therapies, or other immunosuppressant/immunomodulators agents or any other topical or systemic treatment for HS.
- Any surgery for HS including, but are not limited to, the following:
  - Incision and drainage
  - Deroofing
  - Lesion ablation (electrosurgery)
  - Local excision
- Phototherapy (laser and pulsed light therapy) or tanning beds.
- Topical antiseptics (eg, diluted bleach bath or washes containing chlorhexidine gluconate or benzoyl peroxide).

In addition, the following therapies are not permitted during the study:

- Strong systemic CYP3A4 inhibitors.
- Live-attenuated vaccination during the DBVC period.  
Note: COVID-19 vaccination is permitted
- Any investigational medication other than the study drug.

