### **8.1.2. Screening Procedures**

Screening is the interval between signing the ICF and the day the participant is enrolled in the study (Day 1). Screening may not exceed 28 days. Assessments that are required to demonstrate eligibility may be performed over the course of 1 or more days during the screening process.

Procedures conducted as part of the participant's routine clinical management (eg, blood counts or physical examinations) and obtained before signing of the ICF may be used for screening or baseline purposes provided that the procedure meets the Protocol-defined criteria and has been performed in the timeframe of the study (ie, within 28 days or less prior to Day 1). For participants who are enrolled in the study, information associated with eligibility requirements must be entered into the appropriate eCRF pages.

Results from the screening visit evaluations will be reviewed to confirm eligibility before randomization and the administration of study drug. Tests with results that fail eligibility requirements may be repeated once during screening if the investigator believes the results to be in error. For screening assessments that are repeated, the most recent available result before randomization will be used to determine eligibility.

See Sections [5.4](#) and [5.5](#) for information regarding screen failures and replacement of participants, respectively.

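### Exclusion 7 sets no pre-baseline washout for intralesional corticosteroids, lesional HS procedures or laser/light therapy, all banned on study, so baseline AN counts can follow treatment by only days

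*Protocol*

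**What the plan says.** Criterion 7 of Protocol Section 5.2 excludes "Use of any of the following treatments within the indicated washout period before the baseline visit". Seven items follow. Two come near local HS treatment:

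- 7c, four weeks: "systemic corticosteroids or adrenocorticotropic hormone analogs, cyclosporin, methotrexate, azathioprine, or other systemic immunosuppressive or immunomodulating agents". Its corticosteroid entry is limited to the systemic route.
- 7f, two weeks: "topical therapy for HS (eg, topical antiseptics, topical antibiotics, topical corticosteroids, topical calcineurin inhibitors, other topicals". It is limited to the topical route.

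Section 6.6.3 lists what is not permitted during the study. It includes "topical or intralesional corticosteroids, topical calcineurin inhibitors, systemic corticosteroids, methotrexate, dapsone, metformin, tretinoids/retinoids" and, separately, "Any surgery for HS including, but are not limited to, the following", followed by incision and drainage, deroofing, ablation and excision. Laser and pulsed light therapy are also on the list. Section 4.1 says that a participant treated on study with drainage or an intralesional injection is regarded as a nonresponder and discontinued.

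Three other rules bear on timing:

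- Inclusion criterion 4 sets its limits on "The AN count at the screening AND baseline visits", with a total of 3 to 10 and no draining tunnels.
- Inclusion criterion 5, on baseline pain or itch, states that "data from a minimum of 4 out of 7 days directly prior to Day 1 is needed".
- Section 8.1.2 gives only an upper limit for the lead-in: "Screening may not exceed 28 days".

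**The concern.** The plan treats injection or drainage of a lesion as important enough to end participation once treatment has begun, yet permits either a few days before the baseline count. The same criterion asks for two weeks off a topical antiseptic. The documents give no reason for the difference. The situation is foreseeable: Protocol Section 2.1 names intralesional steroid injection and surgery among HS treatments, and SAP 6.1.2 plans to summarise prior incision and drainage and deroofing.

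The baseline count is at stake. Change in AN count, AN50 to AN100, HiSCR and IHS4 change are all measured from it, and the primary MMRM adjusts for baseline only through two strata (3 to 4, and 5 to 10). An injected lesion may be counted at baseline while already resolving. A drained one may be absent at baseline and return later. Counts are low, so one lesion can matter: AN50 needs a Week 16 count of 2 or less from a baseline of 4, but 1 or less from a baseline of 3. One lesion also separates the strata (5 against 4).

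**Working it through.** **Step 1. Compare the two lists.**

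| Treatment | Banned on study (Section 6.6.3) | Washout in 7a to 7g |
|---|---|---|
| Intralesional corticosteroid | Yes | None: 7c is systemic, 7f is topical |
| HS procedures (drainage, deroofing, ablation, excision) | Yes | None |
| Laser or pulsed light | Yes | None |
| Topical antiseptic, for comparison | Yes | 2 weeks (7f) |

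Reading 7f broadly enough to reach injections does not work, because Section 6.6.3 itself names topical and intralesional corticosteroids as separate routes. The remaining items of criterion 7 concern biologics, JAK or TYK2 inhibitors, CYP3A4 inhibitors, systemic antibiotics with live vaccines and sedating antihistamines, and opioids.

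**Step 2. Look for a window elsewhere.** Section 6.6.2 has a window starting 14 days before baseline, but its only entry is stable prescription medication for chronic conditions. Exclusion 4 concerns illnesses and conditions, not recent HS treatment. Section 6.6 records HS treatments from the previous year without making them an eligibility matter. None supplies a washout.

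**Step 3. Find the shortest permitted interval.** Suppose the Section 6.6.3 ban runs from consent.

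- No minimum screening length is stated.
- The diary starts on the day of screening and is completed each evening (Sections 8.1.4 and 8.2.4.1). Four scores among the seven days before Day 1 can come from Days -4 to -1, so screening can begin on Day -4.
- Treatment the day before consent then falls on Day -5. With no Day 0, that is about 5 days before the baseline count.

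If the ban instead starts with study treatment, the interval can be shorter still.

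**Step 4. Illustrate the size.** The documents give neither the frequency of recent treatment nor the SD of change, so the only input taken from them is 30 per arm (about 60, randomised 1:1). Assumed: SD of change 3; a share p of 0.1 to 0.2 recently treated; a shift d of 1 to 2 lesions for each.

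SE = sqrt(2 × (SD² + V) / 30), with V = p(1 − p)d² if all shifts go one way, and V = p·d² if half go up and half down.

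| Case (SD 3) | V | SE (lesions) | Increase | Equivalent N of 60 |
|---|---|---|---|---|
| No recent treatment | 0 | sqrt(2 × 9 / 30) = 0.775 | – | 60 |
| p 0.1, d 1, one direction | 0.1 × 0.9 × 1 = 0.09 | sqrt(2 × 9.09 / 30) = 0.778 | 0.5% | 60 × 9 / 9.09 = 59.4 |
| p 0.2, d 2, one direction | 0.2 × 0.8 × 4 = 0.64 | sqrt(2 × 9.64 / 30) = 0.802 | 3.5% | 60 × 9 / 9.64 = 56.0 |
| p 0.2, d 2, mixed | 0.2 × 4 = 0.80 | sqrt(2 × 9.80 / 30) = 0.808 | 4.3% | 60 × 9 / 9.80 = 55.1 |

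Varying the SD gives 0.3% (SD 4, V 0.09: sqrt(16.09 / 16)) to 9.5% (SD 2, V 0.80: sqrt(4.80 / 4)). This is a single-visit two-group calculation, not the planned MMRM.

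**Step 5. Bias.** The treatment in question precedes randomisation, so its frequency and effect on the count are equal between arms in expectation.

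**The case against.** The case for leaving the text alone has several parts.

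- **The study ban may already cover screening.** Section 4.2 dates the start of the study from the first participant's consent, which supports reading the Section 6.6.3 ban as running from consent. That would close the screening period, but not the days just before consent.
- **Five days is an extreme.** Eligibility depends on central laboratory results, and Section 8.3.4.2 warns that serology takes time. This makes longer screening likely but fixes no minimum.
- **Other rules catch part of the problem.** Treatment accompanied by systemic antibiotics, topical antibiotics or antiseptics, or opioids within two weeks of baseline is excluded by 7e, 7f or 7g. Inclusion 4 still requires at least three lesions at both visits. These limit the gap without closing it.
- **No consequence is shown.** The trial was not sized on power (Section 10.1), so no stated power is lost, and every input to the illustration except the arm size is assumed. This stands: the calculation shows what the effect might be, not that it occurs.
- **The mechanism is uneven.** It is plausible for injection and drainage. The documents give no mechanism for laser or light therapy, and an excised lesion is absent at both baseline and Week 16 unless it recurs. This also stands; those treatments belong in the line for consistency with Section 6.6.3.
- **Reporting is largely planned.** SAP 6.1.2 summarises prior HS surgery and prior HS therapy by treatment group, and Listing 2.4.6 covers prior HS medications. Only recency would be new.

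A reader might extend the argument to every agent banned in Section 6.6.3. Retinoids are arguably within the immunomodulating agents of 7c. Dapsone, metformin and aldactone are also banned and not named in criterion 7, so a ban on study does not by itself show that the plan intended a washout. The point here is confined to treatments applied to the lesions or affected skin.

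**Conclusion.** The gap holds on the text. Criterion 7 is a closed list, no other section supplies a window, and an injection or drainage about five days before baseline is permitted even on the reading of Section 6.6.3 most favourable to the plan. The consequence is some added noise in the primary endpoint and the other count-based measures. It merits consideration rather than being a serious flaw.

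Two stronger conclusions are tempting and unsupported. One is that the gap biases the comparison with vehicle: the exposure precedes randomisation, so only chance imbalance is possible, although with about 60 participants that can occur. The other is that the trial loses a known amount of precision: the 0.5% to 4.3% range (0.3% to 9.5% across SDs of 2 to 4) depends on the assumed frequency, shift and SD, and the true size cannot be calculated from the documents.

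**What to change.** Add one line to criterion 7 with an explicit washout before baseline for intralesional corticosteroids, HS procedures, and laser or light therapy. Four weeks would match 7c; the two weeks of 7f is the least that would be consistent with the rest of the criterion. The exact length is a clinical judgement that the documents do not settle. Systemic retinoids need not be added.

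The cost is a slightly narrower entry window. Four weeks equals the 28-day screening maximum, so someone treated just before consent could still qualify if screening runs its full length and the other criteria are met.

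If enrolment is complete, extend the prior surgery and therapy summary in SAP 6.1.2 to show, by arm, how many participants had any of these treatments within the chosen window before Day 1. Prior HS treatments and surgical procedures are already collected (Protocol Sections 6.6 and 8.1.5.2). Section 8.1.5.2 does not expressly promise procedure dates, so the table can be produced only where dates were captured. The cost is one additional baseline tabulation.
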